IgE FEIA			X																				Section 8.6.1		
Blood for serum and plasma biomarkers			X				X		X		X		X		X		X		X				Section 8.6.1		
Blood for RNA transcriptomic profiling			X				X		X		X		X		X		X		X				Section 8.6.1		
Nasal epithelial lining fluid for PK and Exploratory biomarkers		X ^o	X				X		X								X ⁿ		X				Section 8.6.1		
Staph A Nasal Culture			X						X								X						Section 8.6.1		

Table 1 Schedule of Activities - Screening, Randomisation, Treatment Period, and Follow-Up

Assessment / Activity	Screening	Run-in	Randomisation	Treatment Period																EOT/ IPD	FU all ^d		Additional FU 1 st 200 participants ^c		UNS ^e	Details in CSP section or Appendix
Visit	V1	V2	V3	V4 📞 ^b	V5	V6	V7	V8	V9	V10	V11	V12	V13	V14	V15	V16	V17	V18 📞 ^b	V19	V20 📞 ^b	V21					
Week	-5	-2	0	2	4	8	12	16	20	24	28	32	36	40	44	48	52	58	64	70	76					
Visit window (days) ^a	N/A	±5	±5	±5	±5	±5	±5	±5	±5	±5	±5	±5	±5	±5	±5	±5	±5	±7	±7	±7	±7	N/A	N/A			
Staph A enterotoxin Specific IgE status (only participants in the sub-study) ^o				X																			Section 8.6.1			
Nasal biopsy - tissue for histology and RNA transcriptomics (only participants in the sub-study) ^o				X ^p																			Section 8.6.1			
Genomics Initiative optional, exploratory genetic sample ^q				X																			Section 8.7; Appendix D			
Randomisation, Investigational Product Administration and INCS Management																										
Randomisation				X																			Section 4.1			

Table 1 Schedule of Activities - Screening, Randomisation, Treatment Period, and Follow-Up

Assessment / Activity	Screening	Run-in	Randomisation	Treatment Period															EOT/ IPD	FU all ^d		Additional FU 1 st 200 participants ^c		UNS ^e	Details in CSP section or Appendix
Visit	V1	V2	V3	V4 b	V5	V6	V7	V8	V9	V10	V11	V12	V13	V14	V15	V16	V17	V18 b	V19	V20 b	V21				
Week	-5	-2	0	2	4	8	12	16	20	24	28	32	36	40	44	48	52	58	64	70	76				
Visit window (days) ^a	N/A	±5	±5	±5	±5	±5	±5	±5	±5	±5	±5	±5	±5	±5	±5	±5	±5	±7	±7	±7	±7	N/A	N/A		
IP Administration ^r			X		X	X	X	X	X	X	X	X	X	X	X	X							Section 6.1		
Home IP Administration by HCP (optional) ^s									X	X		X	X		X	X	X							Section 6.2.3	
INCS Distribution ^v	X	X	X		X	X	X	X	X	X	X	X	X	X	X	X	X		X			X	Section 6.4.1		

^a All visits to be scheduled from the date of randomisation, not from the date of previous visit.

^b Visits 4, 18 and 20 is a phone/remote visit (').

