- If SCS is used for treatment of NP for ≥ 3 consecutive days, a CT scan and a nasal endoscopy assessment of NPS should be performed prior to first course of treatment with SCS (unless the subject has already had a CT scan prior to a NP surgery post randomisation). If no such assessment is available, an unscheduled visit should be scheduled to obtain those assessments.
- If SCS use for treatment of any other reason than NP is close to V10 (Week 24) or V17 (Week 52), the visit should be rescheduled at least 2 weeks after the last dose of SCS.
- If SCS will be used for any other reason than NP, the investigator is recommended to consult with the AstraZeneca study physician.

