- If two non-missing values are recorded on the same day and have a different assessment time, the value with the earliest assessment time will be selected for analysis at that visit.
- If two non-missing values (for continuous variables) are recorded on the same day and have no assessment time associated with at least one of them, or the same assessment time associated with both of them, the average of the two values will be selected for analysis at that visit. For categorical variables in this situation, the worst case will be used.
- If there are multiple ADA samples in the same visit window with both positive and negative results, the sample with a positive result and the highest titre value will be selected.

If a participant has no value within a particular visit window, then the participant will have a missing value at that visit in summaries and analysis.

The same visit window definitions below will be used regardless of whether the planned treatment period or the on-treatment period is used for analysis (see Section 3.1.3). In practice, each data record in the planned treatment period will be first identified, and then further flagged according to whether it is on-treatment or off-treatment. This flag will be used to select all eligible records for subsequent visit windowing, according to whether the derived visits are to be used in a planned treatment period or an on-treatment period analysis. It should be noted that, if treatment was discontinued within a particular visit window, the rules above for handling multiple values within the same visit window could select a different record according to whether a planned treatment period analysis or an on-treatment period analysis is needed.

**Table 1** summarises the visit windows to be used for all variables unless specified otherwise. It corresponds to the full (mostly 4-weekly) protocol scheduling for clinic visits and will be

used for all variables by default, including those variables which are not capture at every clinic visit, unless indicated below that the visit windows in [Table 2](#) or [Table 3](#) should be used. Of note, Week 0 is Day 1 in the analysis following the Clinical Data Interchange Standards Consortium (CDISC) standards, although it is labelled as Day 0 in the CSP.

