**Table 1. Visit Windows – All Variables**

Time Point	Target Day	Visit Window
Baseline (Week 0)	See Section 3.1.1 for baseline definitions	
Week 2	15	2-21
Week 4	29	22-42
Week 8	57	43-70
Week 12	85	71-98
Week 16	113	99-126
Week 20	141	127-154
Week 24	169	155-182
Week 28	197	183-210
Week 32	225	211-238
Week 36	253	239-266
Week 40	281	267-294
Week 44	309	295-322
Week 48	337	323-350
Week 52	365	351-378
Follow-up	407	379-427
Week 58		
Follow-up	449	428-469
Week 64		
Follow-up	491	470-511
Week 70		
Follow-up	533	512-553
Week 76		

**Table 2** summarises the adjusted analysis-defined visit windows for NPS and variables in which the sparsest scheduling is planned in the protocol. These variables include: WPAI, ECG, spirometry, FeNO, ACQ-6, and total IgE.

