**Table 2 Visit Windows – NPS and Sparse protocol schedule**

Time Point	Target Day	Visit Window
Baseline (Week 0)	See Section 3.1.1 for baseline definitions	
Week 4	29	2-56
Week 12	85	57-126
Week 24	169	127-210
Week 36	253	211-308
Week 52	365	309-406
Follow-up	449	407-490
Week 64		
Follow-up	533	491-574
Week 76 (only NPS, ECG, spirometry, ACQ-6)		

**Table 3** summarises the visit windows which will be used for NCS and other items in the NPSD which will be summarised every two weeks (bi-weekly).

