**Table 3 Visit Windows – NPSD (including NCS)**

Time Point	Target Day	Visit Window
Baseline (Week 0)	See Section 3.1.1 for baseline definitions	
Week 2	15	2-15
Week 4	29	16-29
Week 6	43	30-43
...	...	...
Week 52	365	352-365
...	...	...
Follow-up	533	520-533
Week 76		

In all cases above, no time points will be presented in summary tables or included in statistical analysis which do not correspond to the time points scheduled in the protocol for the variable in question.

For CT scan, the visit window for Week 52 will include Days 1 – 490.

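### SAP Table 1 closes Week 52 at Day 378, so a visit postponed under Protocol 8.1.4 can have observed UPSIT, NPIF and possibly SNOT-22 values imputed

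*Protocol*

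**What the plan says.** Protocol 8.1.4 covers SCS given for a reason other than nasal polyps (NP) close to V10 (Week 24) or V17 (Week 52): "the visit should be rescheduled at least 2 weeks after the last dose of SCS". It sets no upper limit on the delay and does not define how near counts as close. Otherwise the calendar is fixed: "All visits to be scheduled from the date of randomisation, not from the date of previous visit" (Protocol 1.3, footnote a), with a ±5-day window at V17.

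SAP 3.1.4 sets database visit labels aside and places each value by day. Its windows for Week 52 differ by variable:

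- Table 1 is "used for all variables by default, including those variables which are not capture at every clinic visit". UPSIT, NPIF and SNOT-22 are not named for Table 2 or Table 3, so they fall here. Week 52 reads "Week 52 365 351-378" (target day, then window) and Week 58 reads "Follow-up 407 379-427".
- Table 2, for NPS, spirometry and some others: "Week 52 365 309-406".
- Table 3, for the diary including the nasal congestion score (NCS): "Week 52 365 352-365".
- CT: "For CT scan, the visit window for Week 52 will include Days 1 – 490".

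A participant with no value inside the window is missing at that visit. SAP 4.2.6.1 imputes missing values up to Week 52 under missing at random. SAP 4.2.7.1.2, 4.2.8.2 and 4.2.8.5 carry that method to SNOT-22, UPSIT and NPIF.

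**The concern.** The protocol instructs sites to hold the Week 52 visit late in one situation, and the SAP has no rule that recognises it. NPS and CT have windows wide enough to absorb the delay; the Table 1 variables do not. Measurements from a single visit can therefore be split: the endoscopy counts as Week 52, while the smell test and nasal flow taken the same day are labelled Week 58 and replaced at Week 52 by imputed values. Imputation stops at Week 52, so the real measurement does not inform its own replacement.

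For UPSIT and NPIF the loss is complete. Neither is scheduled at Week 58 (Protocol 1.3 and 8.1.7), and SAP 3.1.4 presents and analyses only time points scheduled for the variable. SNOT-22 matters more because it is a Level 2 key secondary endpoint, but its exposure is conditional, as set out below.

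**Working it through.** **Plan's own figures.** The SAP counts randomisation as Day 1, so the Week 52 target is 52 × 7 + 1 = 365, as stated. V17 at ±5 days is Days 360-370. Table 3 is the 14 days ending on target: 365 - 13 = 352, as stated.

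**Midpoint check.** In Table 1 each later window opens on the midpoint of adjacent targets: (15 + 29)/2 = 22, (29 + 57)/2 = 43, and so on to (337 + 365)/2 = 351; then (407 + 449)/2 = 428, (449 + 491)/2 = 470, (491 + 533)/2 = 512. All match the table. The exception is (365 + 407)/2 = 386, where the table opens Week 58 at 379. Table 2 follows the rule throughout, for example (365 + 449)/2 = 407. Days 379-385 are 14-20 days from the Week 52 target and 22-28 days from the Week 58 target, yet are labelled Week 58. That applies to any late visit, not only steroid cases.

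**Postponed visit.** Earliest visit = the later of Day 365 and (last dose day + 14).

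| Last non-NP SCS dose | Earliest visit | Table 1 label | NPS label |
|---|---|---|---|
| Day 352 | Day 366 | Week 52 | Week 52 |
| Day 364 | Day 378 | Week 52 | Week 52 |
| Day 365 | Day 379 | Week 58 | Week 52 |
| Day 371 | Day 385 | Week 58 | Week 52 |
| Day 392 | Day 406 | Week 58 | Week 52 |
| Day 393 | Day 407 | Week 58 | Week 64 |

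A delay longer than the minimum moves earlier last doses out as well. The value is lost to Week 52 only if no other value for that variable falls in Days 351-378.

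**SNOT-22 in the Week 58 window.** As the schedule reads, SNOT-22 is also marked at V18 (Day 407 ± 7). A Day 379 value is 28 days from target and the V18 value at most 7, so the closest-to-target rule drops the former.

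**V10.** A last dose on Day 169 gives Day 183, which is Week 28 in Table 1 but still Week 24 for NPS (to Day 210). The Table 1 boundary is on pattern here, (169 + 197)/2 = 183; only the postponement is unhandled.

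**How many.** The documents give no rate of non-NP SCS. Assume 0.1-0.5 courses per participant-year, 7-day courses and the minimum delay. The last dose is on Day 365 or later if the course starts on Day 359 or later, and it must start by the day V17 would have taken place.

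- V17 due on Day 365: 7 start days; 7/365 × 0.1 to 0.5 = 0.2-1.0%, about 1-4 of 400.
- V17 due on Day 360 to Day 370: 2 to 12 start days; 0.1-1.6% overall.

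Longer courses or delays raise this.

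**Power.** For SNOT-22 with effect 17.4, SD 26.8, 200 per arm and two-sided 1%: SE = 26.8 × √(2/200) = 2.68; 17.4/2.68 - 2.576 = 3.92; power above 0.999 (stated: at least 95%). With 10% of values lost, 180 per arm, it is still above 0.999.

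**NCS timing.** For a last dose on Day 352 or later, all of Days 352-365 precede the end of the two-week interval. NPS at the earliest postponed visit is read 1-41 days after Day 365 for last doses on Days 352-392.

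**The case against.** The strongest reply is that SNOT-22 may not move with the visit. It is completed on the ePRO device, Protocol 8.1.2 describes at-home assessments that are done on site only if still outstanding, and the schedule marks SNOT-22 at telephone visits. A value near Day 365 may therefore exist. This stands: the EOT order of assessments lists ePRO at the visit, but the documents do not settle the matter, so a reader who infers that SNOT-22 is always lost goes too far. The reply does not rescue NPIF, which uses the on-site MasterScope, or UPSIT, which Protocol 7.1.1 does not have completed at home after treatment discontinuation.

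Second, Days 351-378 has the same 28-day width as Weeks 8 to 48, so Day 378 may be deliberate. That explains the number but not why Days 379-385 go to the more distant visit. It is also fair that Day 385 alone covers last doses only up to Day 371.

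Third, the consequences are small. NPS, FEV1 and LMK are already covered, UPSIT and NPIF lie outside the testing hierarchy, and imputation would draw on Week 48 and earlier data for SNOT-22. All of this stands.

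A reader might also infer that NCS data are discarded or wrong. They are not: the diary is kept daily whatever the visit date, and Protocol 9.4.1.1 applies treatment policy to steroids for co-morbid conditions. Only the timing relative to the steroid course differs from NPS. That an arm imbalance in such steroids would bias NCS but spare NPS is not shown by anything in the documents.

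**Conclusion.** The mismatch is real and unreconciled, but narrow. It arises when the last non-NP SCS dose is on Day 365 or later, or when the delay exceeds the minimum. It then turns observed UPSIT and NPIF values, and SNOT-22 if completed at that visit, into imputed ones at Week 52, while NPS from the same visit is kept.

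The estimate of about 1-4 of 400 rests wholly on the assumed SCS rate, 7-day courses, the minimum delay and a visit otherwise due on Day 365. Applying the same rates to a 28-day span would give 28/365 × 0.1 to 0.5 = 0.8-3.8%, or 3-15 of 400. That is too wide, because it counts courses that end before Day 365 or start after V17 would have taken place.

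Power and the co-primary analyses are not threatened. The case for change is coherence and avoiding needless imputation: a cheap improvement, not a defect in the trial's main conclusion.

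**What to change.** In SAP 3.1.4:

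1. Set the Table 1 Week 52 window to Days 351-385 and Week 58 to Days 386-427. This restores the midpoint rule and covers minimum-delay visits for last doses up to Day 371.
2. For visits postponed under Protocol 8.1.4 with no value in that window, let SNOT-22, UPSIT and NPIF count as Week 52 up to Day 406, as NPS does, with precedence over Week 58. This covers last doses up to Day 392.
3. Reconcile the same edge at V10, for instance with a matching rule up to Day 210, the NPS limit for Week 24.
4. State whether SNOT-22 moves with a postponed visit.

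Keep the primary NCS window at Days 352-365. Tying it to the postponed visit would let a post-randomisation event set a co-primary window and could swap on-steroid days for later ones, which sits badly with treatment policy. A visit-aligned diary mean could be a sensitivity analysis only.

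The cost is SAP wording, settled before unblinding. A few Week 52 values would be taken 2-6 weeks late (Days 379-406 are 14-41 days after target). Item 2 overlaps the Week 58 window, hence the precedence rule, and needs a stated exception to the SAP's bar on visit labels so that postponed visits can be identified.

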8.1.5 Spirometry (Asthma/AERD/NSAID-ERD Participants Only)

8.1.5.1 General Requirements

Lung function (FEV1, FEF 25-75% and FVC) will be measured by spirometry at the study site using equipment provided by a central vendor. The MasterScope is a system which will be used on-site to perform and record results for procedures including, but not limited to, spirometry, NPIF and FeNO.

Spirometry will be performed by the Investigator or authorised delegate according to

American Thoracic Society/European Respiratory Society (ATS/ERS) guidelines or local guidelines ([Graham et al 2019](#))

The MasterScope kit will include a spirometer handle which will be used to record spirometry values at the site. The vendor providing central spirometry is responsible for assuring that the spirometer meets ATS/ERS recommendations and that the study centre personnel who will be performing the testing are properly certified. Spirometry calibration will be detailed in a separate spirometry procedures manual.

Important!

- Participants should avoid engaging in strenuous exertion for at least 30 minutes prior to all lung function assessments at the centre.
- Participants should avoid eating a large meal for at least 2 hours prior to all lung function assessments at the centre.
- Participants should withhold their usual maintenance therapies on the day(s) when lung function testing is being performed as below:
 - SABAs should be withheld at least 6 hours prior to scheduled spirometry at site.
 - Twice daily LABA or LAMA-containing therapies should be withheld for at least 12 hours prior to scheduled spirometry at site.
 - Once daily LABA or LAMA-containing therapies should be withheld for at least 24 hours prior to scheduled spirometry at site
 - LTRA should be restricted for at least 24 hours prior to scheduled spirometry at site.
 - Twice daily theophylline should be withheld for at least 12 hours prior to scheduled spirometry at site.
 - Once daily theophylline for at least 24 hours prior to scheduled spirometry at site

Note: If any of the above restrictions are not met, the spirometry assessment should be rescheduled within the allowed visit window

Time of day for scheduled centre visit spirometry

Spirometry testing should be done according to the SoA. Spirometry testing must be initiated in the morning between 6:00 AM and 11:00 AM during the randomisation visit (Visit 3).

All spirometry assessments should be performed within \pm 1.5 hours of the time it was performed during Visit 3. For example, if the Visit 3 spirometry was started at 8:00 AM, then all subsequent spirometry testing needs to be initiated between 6:30 AM and 9:30 AM.

Spirometry techniques

Detailed procedures for performing spirometry will be described in a separate instruction

manual. Details regarding assessment of the quality of spirometry and the best test report process will also be detailed in the manual.

Spirometry references

The Global Lung Function Initiative (GLI) equations will be used to determine the Predicted Normal Values (PNV) and are pre-programmed into the spirometer ([Quanjer et al 2012](#)) FEV₁, expressed as percent of the PNV, will be calculated as follows:

$$\text{FEV}_1\% \text{ of PNV} = (\text{FEV}_1 \text{ measured}/\text{FEV}_{1\text{PNV}}) \times 100$$

Record Keeping

A signed and dated copy of the pre-BD printout must be kept at study centre for source data verification. The printout must be marked with the study code, enrolment code, date and time of measurement, and visit number. If a printout cannot be printed, the mean value of the measurements will be recorded in the participant's charts.

8.1.6 FeNO (Asthma/AERD/NSAID-ERD Participants Only)

Airway inflammation will be evaluated using a standardised single-breath FeNO test in accordance with the SoA. A single exhalation technique recommended by the manufacturer will be followed ([Alving et al 2017](#)).

Participants will be asked whether they have had a respiratory infection in the 2 weeks prior to the measurement. The FeNO measurements will not be performed within 2 weeks of a respiratory infection. The FeNO test will be performed prior to spirometry. Participants should not eat or drink 1 hour prior to having the FeNO test. Participants should not use their rescue SABA medication (eg, albuterol/salbutamol) within 6 hours of the measurement. Inhaled BDs (including ICS/LABA) should be withheld for the effect duration specific to the BD as described in the spirometry section. If not, the assessment should be postponed till after the required time has passed since the meal or drink or the visit must be rescheduled within the allowed visit window.

The NIOX VERO® Airway Inflammation Monitor will be used to measured FeNO. Instructions for use of this monitor will be provided in a separate user's manual.

NIOX VERO® sensors will be replaced as recommended by the manufacturer. The vendor supplying the equipment will be responsible for ensuring that the equipment and procedures for the measurement of FeNO are validated prior to the start of the study.

8.1.7 Nasal Peak Inspiratory Flow

Nasal peak inspiratory flow (NPIF) evaluation represents a physiological measure of the air flow through both nasal cavities during forced inspiration expressed in liters per minute. Nasal

inspiration correlates most with the participative feeling of obstruction and is the best validated technique for monitoring nasal flow in clinical trials.

A minimum of 3, up to a maximum of 8NPIF efforts will be performed by the participant; all values will be recorded by the participant on the MasterScope and the highest value will be used for evaluation.

The NPIF will be performed at enrolment/screening V1 (Week -5), V3 (Week 0), V7 (Week 12), V10 (Week 24), V13 (Week 36), V17 (Week 52), V19 (Week 64), V21 (Week 76).

The nasal flow is expressed in liters per minute, and consecutive measurements are performed.

Taking the best of 3 outcomes with less than 10% variation is considered to be the best means of expression of the result ([Scadding et al 2011](#)).

8.2 Safety Assessments

Planned time points for all safety assessments are provided in the SoA ([Table 1](#)).

8.2.1 Physical Examinations

Investigator's should pay special attention to clinical signs related to previous serious illnesses as new or worsening abnormalities may qualify as AEs, see section [8.3.5](#) for details.

- A complete physical examination will be performed and include assessments of the following; general appearance, respiratory, cardiovascular, abdomen, skin, head and neck (including ears, eyes, nose and throat), lymph nodes, thyroid, muscular-skeletal (including spine and extremities) and neurological systems.
- A brief physical examination will include, at a minimum, assessments of the skin, lungs, cardiovascular system, and abdomen (liver and spleen). For the brief physical assessment only, information on whether the assessment was performed or not is to be recorded.

Physical examination will be performed at timepoints as specified in the SoA.

8.2.2 Vital Signs

Vital signs will be performed at timelines as specified in the [SoA](#).

Vital signs are to be taken prior to IP administration, and if possible, before blood draw.

Body temperature, pulse rate, respiratory rate, and blood pressure (BP) will be assessed:

- Body temperature will be measured in Celsius before IP administration in accordance with local standards;

- Blood pressure and pulse measurements will be assessed in sitting position with a completely automated device. Manual techniques will be used only if an automated device is not available;
- Blood pressure and pulse measurements should be preceded by at least 5 minutes of rest for the participant in a quiet setting without distractions (eg, television, cell phones);
- Pulse rate will be obtained before blood pressure if the manual technique is used.
- Respiration rate will be obtained after participant has been resting for at least 5 minutes, by counting number of breaths (how many times the chest rises) for 1 minute.

